### 6.2.1 CMP-001 Associated Adverse Events (see Table 2)

The safety profile for intratumoral CMP-001 in combination with Pembrolizumab has been reported in melanoma clinical trial (N=159) and treatment related adverse events described in detail in Investigator Brochure version 07 (26July2021). Allergic reactions of an immediate type, including anaphylaxis, have been observed after CMP-001 administration. Investigators must be vigilant in identifying and managing these disorders according to institutional guidelines.

#### 6.2.1.1 Injection Site Reactions

If subjects develop inflammation at the injection site this may be managed using cold compresses and/or acetaminophen or non-steroidal anti-inflammatory agents. If flu-like symptoms (i.e., fever, myalgia, and headache) arise, these may be managed using acetaminophen or non-steroidal anti-inflammatory agents.

### **6.2.1.2 Prophylaxis and Treatment of Adverse Events Associated with CMP-001**

CMP-001 is designed to specifically activate TLR9, which is expressed in the endosomes of pDCs. Upon activation through TLR9, pDCs secrete cytokines, including type I IFNs and associated Th1-promoting cytokines. Given this mechanism of action, it is expected that the AE profile associated with CMP-001 administration may be similar to that seen after administration of IFNs (eg, flu-like symptoms such as fever and headaches). The recommended algorithm for the treatment of AEs associated with CMP-001 (**Figure 2**) is currently being studied in Regeneron-sponsored studies. The first line of treatment for hypotension unresponsive to supportive care such as fluids, is stress dose steroids. Additional treatment measures may include the use of drugs targeting specific cytokines believed to be involved in the development of cytokine release syndrome associated hypotension.

[figure not shown]

Figure 2: Recommended Treatment Algorithm for Cytokine Release Symptoms

### **6.2.2 Pembrolizumab-Associated Adverse Events**

AEs associated with pembrolizumab exposure may represent an immunologic etiology. These immune-related AEs (irAEs) may occur shortly after the first dose or several months after the last dose of pembrolizumab treatment and may affect more than one body system simultaneously. Therefore, early recognition and initiation of treatment is critical to reduce complications. Based on existing clinical study data, most irAEs were reversible and could be managed with interruptions of pembrolizumab, administration of corticosteroids and/or other supportive care. For suspected irAEs, ensure adequate evaluation to confirm etiology or exclude other causes. Additional procedures or tests such as bronchoscopy, endoscopy, skin biopsy may be included as part of the evaluation. Based on the severity of irAEs, withhold or permanently discontinue pembrolizumab and administer corticosteroids. Dose modification and toxicity management guidelines for irAEs associated with pembrolizumab are provided in Table 7.

**Table 7 Dose modification and toxicity management guidelines for immune-related AEs associated with pembrolizumab monotherapy and IO Combinations**

General instructions:
 
 
1. Severe and life-threatening irAEs should be treated with IV corticosteroids followed by oral steroids. Other immunosuppressive treatment should begin if the irAEs are not controlled by corticosteroids.
 
2. Study intervention must be permanently discontinued if the irAE does not resolve or the corticosteroid dose is not <math>\leq 10</math> mg/day within 12 weeks of the last study intervention treatment.
 
3. The corticosteroid taper should begin when the irAE is <math>\leq</math> Grade 1 and continue at least 4 weeks.
 
4. If study intervention has been withheld, study intervention may resume after the irAE decreased to <math>\leq</math> Grade 1 after corticosteroid taper.
 
				
irAEs	Toxicity Grade (CTCAE v5.0)	Action With Pembrolizumab	Corticosteroid and/or Other Therapies	Monitoring and Follow-up
Pneumonitis	Grade 2	Withhold	
 
• Administer corticosteroids (initial dose of 1 to 2 mg/kg prednisone or equivalent) followed by taper
 
	
 
• Monitor participants for signs and symptoms of pneumonitis
 
• Evaluate participants with suspected pneumonitis with radiographic imaging and initiate corticosteroid treatment
 

	Recurrent Grade 2, Grade 3 or 4	Permanently discontinue	
 
• Add prophylactic antibiotics for opportunistic infections
 
	
Diarrhea/Colitis	Grade 2 or 3	Withhold	
 
• Administer corticosteroids (initial dose of 1 to 2 mg/kg prednisone or equivalent) followed by taper
 
	
 
• Monitor participants for signs and symptoms of enterocolitis (ie, diarrhea, abdominal pain, blood or mucus in stool with or without fever) and of bowel perforation (ie, peritoneal signs and ileus)
 
• Participants with <math>\geq</math>Grade 2 diarrhea suspecting colitis should consider GI consultation and performing endoscopy to rule out colitis
 
• Participants with diarrhea/colitis should be advised to drink liberal quantities of clear fluids. If sufficient oral fluid intake is not feasible, fluid and electrolytes should be substituted via IV infusion
 

	Recurrent Grade 3 or Grade 4	Permanently discontinue		

irAEs	Toxicity Grade (CTCAE v5.0)	Action With Pembrolizumab	Corticosteroid and/or Other Therapies	Monitoring and Follow-up
AST or ALT Elevation or Increased Bilirubin	Grade 2 a	Withhold	
 
Administer corticosteroids (initial dose of 0.5 to 1 mg/kg prednisone or equivalent) followed by taper
 
	
 
Monitor with liver function tests (consider weekly or more frequently until liver enzyme value returned to baseline or is stable)
 

	Grade 3 b or 4 c	Permanently discontinue	
 
Administer corticosteroids (initial dose of 1 to 2 mg/kg prednisone or equivalent) followed by taper
 
	
T1DM or Hyperglycemia	New onset T1DM or Grade 3 or 4 hyperglycemia associated with evidence of $\beta$ -cell failure	Withhold d	
 
Initiate insulin replacement therapy for participants with T1DM
 
Administer antihyperglycemic in participants with hyperglycemia
 
	
 
Monitor participants for hyperglycemia or other signs and symptoms of diabetes
 

Hypophysitis	Grade 2	Withhold	
 
Administer corticosteroids and initiate hormonal replacements as clinically indicated
 
	
 
Monitor for signs and symptoms of hypophysitis (including hypopituitarism and adrenal insufficiency)
 

	Grade 3 or 4	Withhold or permanently discontinue d		
Hyperthyroidism	Grade 2	Continue	
 
Treat with nonselective beta-blockers (eg, propranolol) or thionamides as appropriate
 
	
 
Monitor for signs and symptoms of thyroid disorders
 

	Grade 3 or 4	Withhold or permanently discontinue d		
Hypothyroidism	Grade 2, 3 or 4	Continue	
 
Initiate thyroid replacement hormones (eg, levothyroxine or liothyronine) per standard of care
 
	
 
Monitor for signs and symptoms of thyroid disorders
 

	Grade 2	Withhold		
 
Monitor changes of renal function
 

irAEs	Toxicity Grade (CTCAE v5.0)	Action With Pembrolizumab	Corticosteroid and/or Other Therapies	Monitoring and Follow-up
Nephritis: grading according to increased creatinine or acute kidney injury	Grade 3 or 4	Permanently discontinue	
 
Administer corticosteroids (prednisone 1 to 2 mg/kg or equivalent) followed by taper
 
	
Neurological Toxicities	Grade 2	Withhold	
 
Based on severity of AE administer corticosteroids
 
	
 
Ensure adequate evaluation to confirm etiology and/or exclude other causes
 

	Grade 3 or 4	Permanently discontinue		
Myocarditis	Grade 1	Withhold	
 
Based on severity of AE administer corticosteroids
 
	
 
Ensure adequate evaluation to confirm etiology and/or exclude other causes
 

	Grade 2, 3 or 4	Permanently discontinue		
Exfoliative Dermatologic Conditions	Suspected SJS, TEN, or DRESS	Withhold	
 
Based on severity of AE administer corticosteroids
 
	
 
Ensure adequate evaluation to confirm etiology or exclude other causes
 

	Confirmed SJS, TEN, or DRESS	Permanently discontinue		
All Other irAEs	Persistent Grade 2	Withhold	
 
Based on severity of AE administer corticosteroids
 
	
 
Ensure adequate evaluation to confirm etiology or exclude other causes
 

	Grade 3	Withhold or discontinue based on the event e		
	Recurrent Grade 3 or Grade 4	Permanently discontinue		

irAEs	Toxicity Grade (CTCAE v5.0)	Action With Pembrolizumab	Corticosteroid and/or Other Therapies	Monitoring and Follow-up

AE(s)=adverse event(s); ALT= alanine aminotransferase; AST=aspartate aminotransferase; CTCAE=Common Terminology Criteria for Adverse Events; DRESS=Drug Rash with Eosinophilia and Systemic Symptom; GI=gastrointestinal; IO=immuno-oncology; ir=immune related; IV=intravenous; SJS=Stevens-Johnson Syndrome; T1DM=type 1 diabetes mellitus; TEN=Toxic Epidermal Necrolysis; ULN=upper limit of normal.
 
Note: Non-irAE will be managed as appropriate, following clinical practice recommendations.
 
a AST/ALT: >3.0 to 5.0 x ULN if baseline normal; >3.0 to 5.0 x baseline, if baseline abnormal; bilirubin:>1.5 to 3.0 x ULN if baseline normal; >1.5 to 3.0 x baseline if baseline abnormal
 
b AST/ALT: >5.0 to 20.0 x ULN, if baseline normal; >5.0 to 20.0 x baseline, if baseline abnormal; bilirubin:>3.0 to 10.0 x ULN if baseline normal; >3.0 to 10.0 x baseline if baseline abnormal
 
c AST/ALT: >20.0 x ULN, if baseline normal; >20.0 x baseline, if baseline abnormal; bilirubin: >10.0 x ULN if baseline normal; >10.0 x baseline if baseline abnormal
 
d The decision to withhold or permanently discontinue pembrolizumab is at the discretion of the investigator or treating physician. If control achieved or ≤ Grade 2, pembrolizumab may be resumed.
 
e Events that require discontinuation include, but are not limited to: encephalitis and other clinically important irAEs (eg, vasculitis and sclerosing cholangitis).
				

### 6.2.2.1 Dose modification and toxicity management of infusion-reactions related to pembrolizumab

Pembrolizumab may cause severe or life-threatening infusion-reactions including severe hypersensitivity or anaphylaxis. Signs and symptoms usually develop during or shortly after drug infusion and generally resolve completely within 24 hours of completion of infusion. Dose modification and toxicity management guidelines on pembrolizumab associated infusion reaction are provided in Table 8.

**Table 8 Pembrolizumab Infusion Reaction Dose modification and Treatment Guidelines**

NCI CTCAE Grade	Treatment	Premedication at Subsequent Dosing
Grade 1 Mild reaction; infusion interruption not indicated; intervention not indicated	Increase monitoring of vital signs as medically indicated until the participant is deemed medically stable in the opinion of the investigator.	None
Grade 2 Requires therapy or infusion interruption but responds promptly to symptomatic treatment (e.g., antihistamines, NSAIDs, narcotics, IV fluids); prophylactic medications indicated for ≤24 hrs	Stop Infusion. Additional appropriate medical therapy may include but is not limited to: IV fluids Antihistamines NSAIDs Acetaminophen Narcotics Increase monitoring of vital signs as medically indicated until the participant is deemed medically stable in the opinion of the investigator. If symptoms resolve within 1 hour of stopping drug infusion, the infusion may be restarted at 50% of the original infusion rate (e.g. from 100 mL/hr to 50 mL/hr). Otherwise dosing will be held until symptoms resolve and the participant should be premedicated for the next scheduled dose. Participants who develop Grade 2 toxicity despite adequate premedication should be permanently discontinued from further study drug treatment	Participant may be premedicated 1.5h (± 30 minutes) prior to infusion of Pembrolizumab with: Diphenhydramine 50 mg po (or equivalent dose of antihistamine). Acetaminophen 500-1000 mg po (or equivalent dose of analgesic).
Grades 3 or 4 Grade 3: Prolonged (i.e., not rapidly responsive to symptomatic medication and/or brief interruption of infusion); recurrence of symptoms following initial improvement; hospitalization indicated for other clinical sequelae (e.g., renal impairment, pulmonary infiltrates) Grade 4: Life-threatening; pressor or ventilatory support indicated	Stop Infusion. Additional appropriate medical therapy may include but is not limited to: Epinephrine** IV fluids Antihistamines NSAIDs Acetaminophen Narcotics Oxygen Pressors Corticosteroids Increase monitoring of vital signs as medically indicated until the participant is deemed medically stable in the opinion of the investigator. Hospitalization may be indicated. **In cases of anaphylaxis, epinephrine should be used immediately. Participant is permanently discontinued from further study drug treatment.	No subsequent dosing
Appropriate resuscitation equipment should be available at the bedside and a physician readily available during the period of drug administration. For further information, please refer to the Common Terminology Criteria for Adverse Events v4.0 (CTCAE) at http://ctep.cancer.gov		

**Other allowed dose interruption for pembrolizumab**

Pembrolizumab may be interrupted for situations other than treatment-related AEs such as medical / surgical events or logistical reasons not related to study therapy. Participants should be placed back on study therapy within 3 weeks of the scheduled interruption, unless otherwise discussed with the Sponsor. The reason for interruption should be documented in the patient's study record.

## 7.0 TRIAL FLOW CHART

Procedure or Assessment	Screening (Day -21 to -1) a	W1 D1	W2 D1	W3 D1	W4 D1	W5 D1	W6 D1	W7 D1	W10 D1	Every 3 Weeks Post W10 (W13, W16 etc.)	End of Treatment b	30 Day Follow up visit n	Long Term Survival Follow-up o
CMP-001 Dose Number	n/a	1	2	3	4	5	6	7	8	9+	n/a	n/a	n/a
Visit Windows	n/a	n/a	±2 days	±2 days	±2 days	±2 days	±2 days	±2 days	±7 days	±7 days	±7 days	±7 days	± 1 month
Informed Consent	X												
Eligibility Criteria Assessment	X												
Medical History, Demographics, Cancer History including Prior Cancer Medications	X												
Physical Exam c	X	X		X	X			X	X	X	X		
Vital Signs d	X	X	X	X	X	X	X	X	X	X	X		
ECOG Performance Status	X	X		X	X			X	X	X	X		
Body Weight	X	X			X			X	X	X	X		
Height	X												
Electrocardiogram (ECG) e	X	X		X				X			X		
Autoimmune lab panel f	X										X		
Clinical Laboratory Tests (hematology, serum chemistry, urinalysis) g	X	X	X	X	X	X	X	X	X	X	X		
Coagulation Tests (PTT & INR) h		X						X	X	X			
Thyroid Function Tests	X			X				X			X		
Research blood Samples i	X	X		X			X		X	-			
Tumor Biopsy j	X			X			X		X	-			
Urine Pregnancy Test k	X	X			X			X	X	X	X		
Disease Assessment (PET-CT/CT) a, l	X	At W7D1 (or two cycles) and then as clinically indicated											
Adverse Event Monitoring n		Assessed continually from W1D1 through EOT +30 days											
Concomitant Medications		Assessed continually from 28 days prior to first CMP-001 dose through EOT +30 days											
CMP-001 dosing m		X	X	X	X	X	X	X	X	X			
Pembrolizumab Dosing		Pembrolizumab will be given according to pembrolizumab label (every 3 week)											

**Footnotes for Trial Flow Sheet:**

- a. Computed tomography (CT neck/chest/abdomen/pelvis with contrast) or PET-CT scans may be performed  $\leq 3$  weeks prior to first CMP-001 dose but up to 4 weeks will be acceptable. MRI will only be considered in specific situation if needed.
- b. End-of-treatment (EOT) assessments to be performed within 7 days following removal of subject from CMP-001 treatment. Removal of a subject from CMP-001 treatment is defined as the time in which the Investigator decides to discontinue CMP-001 treatment for a subject.
- c. A full physical exam will be conducted at Screening and EOT. The Screening physical exam may be performed up to 72 hours prior to the Week 1 Day 1 (W1D1) visit. If the full physical exam is performed  $>72$  hours prior to the W1D1 visit, then a brief (symptom directed) physical exam must be performed within 72 hours prior to initiation of CMP-001.
- d. For the first five CMP-001 dosing visits, vital signs are to be collected prior to CMP-001 dosing, and at 30 ( $\pm 15$ ) minute intervals for 4 hours post end of CMP-001 dosing. Based upon the discretion of the Investigator, observation periods can be reduced to 1 hour for individual subjects who demonstrate mild to no adverse events. Reduced observation periods can be implemented only after the 6th dose of CMP-001. Vital signs should be performed prior to collection of clinical laboratory tests when they are performed at the same visit. On days that CMP-001 and Pembrolizumab are both given, vital signs should be collected following the administration of CMP-001. When CMP-001 intratumoral injection and pembrolizumab dosing fall on the same day, it is recommended that CMP-001 intratumoral injection precede pembrolizumab dosing.
- e. Electrocardiograms (ECGs) should be obtained at Screening and prior to CMP-001 intratumoral injection at the 1st, 3rd, and 7th CMP-001 injection (on W1D1, W3D1, W7D1), and EOT visit.
- f. Autoimmune lab panel to be collected at Screening and EOT. Table 9
- g. Clinical laboratory tests may be performed up to 72 hours prior to administration of CMP-001.
- h. Partial thromboplastin time (PTT) and international normalized ratio (INR) tests should be obtained, and results reviewed as per schedule above. These may be obtained up to 72 hours prior to administration of CMP-001.
- i. Blood samples (20 ml) for research including exploratory biomarker, immunogenicity studies, and assessment of pharmacodynamics are to be collected at screening and then on following days and times:  
 Blood draw pre-treatment W1D1 or before, W3D1, W6D1, W10D1 prior to dosing with CMP-001 – Additional blood draw with subsequent cycles may be requested.
- j. Archival tumor samples should be identified at Screening, if available for potential access later. Additional tumor biopsies are optional and may be collected at other times then specified below at the discretion of the Investigator. Optional tumor biopsies (fresh frozen when feasible and typically FNA), will be collected prior to starting treatment on W1D1, W3D1, W6D1, W10D1. If pre-treatment biopsy prior to W1D1 treatment not done, it can be scheduled with W2D1 intra-tumor injection.
- k. In women of childbearing age, Urine pregnancy testing should be performed at Screening and prior to 1st CMP-001 injection (W1D1), prior to 4th CMP-001 injection (W4D1), prior to 7th CMP-001 injection (W7D1), followed by every 3 weeks prior to treatment and EOT. A negative test within 72 hours of treatment is acceptable.
- l. CT neck/chest/abdomen/pelvis with contrast or PET-CT scans to assess response will be at W7D1 (or after two cycles) and then as clinically indicated. Subjects may be asked to provide historical scans (scans performed prior to Screening) for informational purposes prior to starting CMP-001 therapy, if available.
- m. The first CMP-001 injection stimulates antibody formation to the VLP of CMP-001 and will be given subcutaneously. Subsequently, CMP-001 should be administered as close to the tumor as possible if intratumoral injection not possible. A window of  $\pm 2$  day is permitted for the CMP-001 dose schedule for the first weekly CMP-001 injections and a window of  $\pm 7$  days is permitted for every 3 week CMP-001 injections. To assure maximum effectiveness, consecutive IT injections of CMP-001 should always be administered at least 96 hours apart. No CMP-001 dose should be skipped. If a CMP-001 dose needs to be delayed due to toxicity the dose should be completed as soon as the toxicity has resolved.
- n. The 30-Day Follow-up (+7 Days) or before new treatment is started is a safety follow up visit that may be conducted in the study clinic OR via phone. The subject should be questioned for any new AEs or ConMeds, no other safety assessments are required unless the Investigator identifies a new safety concern that requires further follow-up. This visit should occur 30 days (+7) after the EOT visit. SAEs that occur within 90 days of the end of treatment or before initiation of a new anti-cancer treatment, whichever comes first should also be followed and recorded.
- o. All subjects will be followed for survival for 2 years ( $3 \pm 1$  month). Survival follow up may be accomplished by visit or phone contact for two years or until subject death, subject consent is withdrawn, subject is lost to follow up or the study is completed.

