## 5.2 Participant Exclusion Criteria

Participants are excluded from the study if any of the following criteria apply:

1. A WOCBP who has a positive urine pregnancy test within 72 hours prior to first dose of study drug. (see Appendix C). If the urine test is positive or cannot be confirmed as negative, a serum pregnancy test will be required.
2. Has received prior therapy with an anti-PD-1, anti-PD-L1, or anti-PD-L2 agent or with an agent directed to another stimulatory or co-inhibitory T-cell receptor (eg, CTLA-4, OX-40, CD137) within 4 weeks of enrollment into this trial.
3. Has received prior systemic anti-cancer therapy including investigational agents within 4 weeks or within 5 half-lives, whichever is shorter, prior to first dose of study drug.

Note: Participants must have recovered from all AEs due to previous therapies to  $\leq$  Grade 1 or baseline. Participants with  $\leq$  Grade 2 neuropathy may be eligible.

Note: If participant received major surgery, they must have recovered adequately from the toxicity and/or complications from the intervention prior to starting study treatment.

4. Has received prior radiotherapy within 2 weeks of start of study treatment. Participants must have recovered from all radiation-related toxicities, not require corticosteroids, and not have had radiation pneumonitis. A 1-week washout is permitted for palliative radiation ( $\leq 2$  weeks of radiotherapy) to non-CNS disease.
5. Has received a live vaccine or live-attenuated vaccine within 30 days prior to the first dose of study drug. Administration of killed vaccines is allowed.
6. Is currently participating in or has participated in a study of an investigational agent or has used an investigational device within 4 weeks, or within 5 half-lives, whichever is shorter, prior to the first dose of study treatment.  
Note: Participants who have entered the follow-up phase of an investigational study may participate as long as it has been 4 weeks, or 5 half-lives, whichever is shorter, after the last dose of the previous investigational agent.
7. Has a diagnosis of primary immunodeficiency disorder or is receiving chronic systemic steroid therapy (in dosing exceeding 10 mg daily of prednisone equivalent) or any other form of immunosuppressive therapy within 7 days prior to the first dose of study drug.

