### **5.4.2 Prohibited Concomitant Medications**

Participants are prohibited from receiving the following therapies during the Screening and Treatment Phase (including retreatment for post-complete response relapse) of this trial:

- Antineoplastic systemic chemotherapy or biological therapy
- Immunotherapy not specified in this protocol
- Chemotherapy not specified in this protocol
- Investigational agents other than pembrolizumab and CMP-001

- Radiation therapy
  - Note: Radiation therapy to a symptomatic solitary lesion or to the brain may be allowed at the investigator's discretion. CMP-001 in this case must be suspended until radiation treatment is completed.
- Live vaccines within 30 days prior to the first dose of study treatment and while participating in the study. Examples of live vaccines include, but are not limited to, the following: measles, mumps, rubella, varicella/zoster, yellow fever, rabies, BCG, and typhoid vaccine. Seasonal influenza vaccines for injection are generally killed virus vaccines and are allowed; however, intranasal influenza vaccines (eg, FluMist®) are live attenuated vaccines and are not allowed.
- Systemic glucocorticoids for any purpose other than to modulate symptoms from an event of clinical interest of suspected immunologic etiology. The use of physiologic doses of corticosteroids may be approved after consultation with the Sponsor.

Participants who, in the assessment by the investigator, require the use of any of the aforementioned treatments for clinical management should be removed from the study. All treatments that the Investigator considers necessary for a participant's welfare may be administered at the discretion of the Investigator in keeping with the community standards of medical care.

Medications or vaccinations specifically prohibited in the exclusion criteria are not allowed during the ongoing study. If there is a clinical indication for any medication or vaccination specifically prohibited during the study, discontinuation from study therapy or vaccination may be required. The final decision on any supportive therapy or vaccination rests with the investigator and/or the participant's primary physician. However, the decision to continue the participant on study treatment requires the mutual agreement of the investigator, the Sponsor and the participant.

There are no prohibited therapies during the Post-Treatment Follow-up Phase.

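### The baseline scan may be up to 4 weeks old and need not follow the last prior anti-cancer therapy, so shrinkage from that therapy could count as a study response

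*Combined protocol and SAP*

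**What the plan says.** - **Scan window (Section 7.0, footnote a).** The baseline CT or PET-CT is due at most 3 "weeks prior to first CMP-001 dose but up to 4 weeks will be acceptable". Section 8.1.3 treats the Screening assessment as the baseline value. Footnote l sets the first response scan at W7D1 or after two cycles, and says scans made before Screening are only informative.
- **Systemic therapy (Section 5.2, exclusion 3).** A patient is excluded for systemic anti-cancer therapy "within 4 weeks or within 5 half-lives, whichever is shorter, prior to first dose of study drug". Exclusion 2 handles checkpoint and similar T-cell agents separately: none "within 4 weeks of enrollment into this trial".
- **Radiotherapy (exclusion 4).** The criterion reads "Has received prior radiotherapy within 2 weeks of start of study treatment", then adds: "A 1-week washout is permitted for palliative radiation" (non-CNS disease).
- **Screening-phase ban (Section 5.4.2).** "Participants are prohibited from receiving the following therapies during the Screening and Treatment Phase"; the list includes systemic chemotherapy, biological therapy and radiation. A note makes an exception: "Radiation therapy to a symptomatic solitary lesion or to the brain may be allowed", at the investigator's discretion. The flow chart places Screening at Day -21 to -1.
- **Use of the response.** Section 4.5 makes objective response rate the primary efficacy endpoint. Appendix F, Table A uses the number of responders to rank and eliminate doses. There is no control arm.

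**The concern.** Response is measured as change from the baseline scan. If a patient is scanned, then receives more anti-lymphoma drug or radiation, and only then starts study treatment, the W7D1 comparison includes the effect of that earlier therapy. Without a control arm, nothing in the data would separate it from the effect of CMP-001 plus pembrolizumab.

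The same response count steers a dose-finding design run in cohorts of three. A misattributed response could keep open a dose that the efficacy rule would have eliminated.

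**Working it through.** **1. How long can therapy follow the scan?**

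Inputs: scan age A, at most 28 days (21 is the usual limit in footnote a); washout W, which is 7 days for palliative radiation, 14 for other radiation, and min(28, 5h) for a systemic drug with half-life h days (exclusions 3 and 4); Screening start on Day -s, with s at most 21 (flow chart).

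- If only the Section 5.2 washouts apply: gap = A - W.
- If the Section 5.4.2 ban also applies from Day -s: gap = A - max(W, s).

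| Prior therapy | W | 5.2 only, A = 28 | 5.2 only, A = 21 | With 5.4.2, s = 21, A = 28 |
|---|---|---|---|---|
| Palliative radiation | 7 | 28 - 7 = 21 | 14 | 28 - 21 = 7 |
| Other radiation | 14 | 28 - 14 = 14 | 7 | 7 |
| Systemic, h = 1 | 5 | 28 - 5 = 23 | 16 | 7 |
| Systemic, h = 3 | 15 | 28 - 15 = 13 | 6 | 7 |
| Systemic, h = 5 | 25 | 28 - 25 = 3 | none | 3 |
| Systemic, h of 5.6 or more | 28 | 0 | none | 0 |

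The last column leaves out the discretionary radiation exception, under which the first two rows return to 21 and 14 days. With 5.4.2 in force over a full Screening period and a scan on Day -21, the gap is 21 - 21 = 0 apart from that exception.

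A later Screening start widens the gap. With s = 10, for example, it is 28 - 10 = 18 days for palliative radiation and 28 - 14 = 14 for other radiation.

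**2. What can one response change?**

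The plan drops a dose unless Pr(efficacy rate < 0.5 | data) < 0.90. With a uniform prior (assumed), x responses in n patients give a Beta(1 + x, 1 + n - x) posterior:

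- 0/3: Beta(1,4), probability 0.9375, eliminated. 1/3: Beta(2,3), 0.6875, kept.
- 1/6: Beta(2,6), 0.9375, eliminated. 2/6: Beta(3,5), 0.773, kept.

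Table A agrees. With no toxicity, 0/3 is E and 1/3 scores 42; 1/6 is E and 2/6 scores 28.

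**3. The plan's own operating characteristics.**

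The design was simulated with 10,000 trials per scenario. The Case A/B/C decision table is not legible in the text, so interval boundaries of 0.236 and 0.359 and a 6-patient cut-off between Cases A and B were assumed.

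- Efficacy 0.10 at both doses, toxicity 0.20: 3.0% total selection and 7.9 patients. Table B gives 1.9 + 1.2 = 3.1% and 7.9.
- Efficacy 0.40/0.50, toxicity 0.20: 84.4% and 15.2 patients. Table B gives 35.8 + 48.8 = 84.6% and 7.6 + 8 = 15.6.

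Total selection agreed within 2 points in every scenario checked. The split between doses differed by up to about 9 points at high toxicity, so only totals are used below.

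**4. Illustration only.**

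Suppose a share c of true non-responders is counted as responding because of earlier therapy, equally at both doses. The apparent rate is 0.10 + 0.90c. True efficacy is 0.10 and toxicity 0.20.

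| Assumed c | Apparent rate | Chance of 0/3 in the first cohort | Chance a dose is selected |
|---|---|---|---|
| 0 | 0.10 | 0.90³ = 73% | 3.0% |
| 0.05 | 0.145 | 0.855³ = 63% | 9.6% |
| 0.10 | 0.19 | 0.81³ = 53% | 19.8% |
| 0.20 | 0.28 | 0.72³ = 37% | 46.6% |

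The values of c have no source in the documents.

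**The case against.** The strongest reply is that Section 5.4.2 already forbids most of this. A minimum washout and a Screening-phase ban can both be obeyed, the stricter one then binds, and 5.4.2 says patients who need a barred treatment should leave the study. A reader of Section 5.2 alone might infer that a patient scanned on Day -27 may stay on an oral drug until Day -5, or be irradiated on Days -20 to -8. The documents do not support that without qualification: over a full 21-day Screening, 5.4.2 bars the drug, and bars the radiation unless the exception applies. This stands, and it limits the point.

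It does not close the gap. The ban does not reach Days -28 to -22, although footnote a accepts a scan from that week. It starts later if Screening does. It has its own radiation exception, and it cannot easily be squared with an express 1-week palliative washout. Footnote l could be read as disqualifying any pre-Screening scan as baseline, but footnote a is attached to Screening and accepts 4 weeks, so the two notes pull apart.

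Other safeguards narrow the risk:

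- Exclusion 2 gives checkpoint and similar agents a 4-week limit with no half-life alternative.
- Inclusion 5 counts lesions in an irradiated area only after shown progression. It does not clearly cover a lesion measured first and irradiated afterwards.
- Exclusion 16 lets the investigator exclude a patient for confounding therapy, but this is discretionary.
- Partial response under Appendix D needs at least a 50% fall in the summed products of up to six masses and no new sites. Radiation to one lesion would often not achieve that in multi-site disease, so radiation is the weaker route.

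Finally, growth between an old scan and first dose biases the other way, so the net direction is not established.

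**Conclusion.** The point holds in limited form. The plan accepts a baseline scan that may predate the end of prior therapy, and its passages disagree on how late that therapy may be given. The exposure is Days -28 to -22 plus the radiation exception if 5.4.2 governs a full Screening period. Otherwise it is up to 21 days (palliative radiation), 14 days (other radiation), or 28 minus 5 half-lives (systemic therapy).

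The consequence is real because one response can move a dose from eliminated to retained. That sensitivity applies to any misclassified response in this design, so it does not measure how large this particular bias is.

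A reader might infer from the illustration that the true false-selection rate is 10% or 20% instead of 3%. The documents do not support that: the carry-over share is assumed and its frequency unknown. Nor do they show that the effect would fall more on 7.5 mg than on 10 mg. The plan's stated 3% is not in error; it presumes that counted responses are due to study treatment. The change is worth making because it is cheap and, by the protocol's own count, 18 patients remain to be enrolled.

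**What to change.** - In footnote a and Section 8.1.3, state that the baseline scan used for response must be obtained after the last dose of prior systemic anti-cancer therapy and the last fraction of radiotherapy, within the existing 4-week window.
- State that lesions irradiated after the baseline scan are not counted for response.
- Reconcile Section 5.4.2 with exclusions 3 and 4 so that they describe the same period. Which washout applies is for the sponsor and investigators; the statistical need is only that the passages agree.
- Reconcile footnote a with footnote l on whether a scan made before Screening can serve as baseline.

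Cost: protocol wording, and a repeat scan for a few patients whose scan was early. Most need only the planned scan timed after their last treatment. The change does not remove delayed shrinkage from therapy that ended before the scan, nor growth between the scan and first dose.
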